Number of Participants:	N=24 (n=12 in Australia and n=12 in Singapore) Accounts for 20% attrition.
Inclusion/Exclusion Criteria:	
INCLUSION CRITERIA:
 
 1. Healthy men, 21-50-year old 2. BMI 18-27.5 kg/m^2 3. Consuming <2 meals of fatty fish/week and no fish oil supplements 4. Ethnicity 
 ○ If Australian site: Australian European 
OR
 
 ○ If Singapore site: Chinese Singaporean 
EXCLUSION CRITERIA:
 
 1. Self-reported history of chronic disease - cancer, type 2 diabetes, cardiovascular disease, liver disease or any condition that may, in the opinion of the principle investigator, influence the study outcomes. 2. Self-reported history of gastrointestinal disease, pancreatic insufficiency, conditions resulting in fat malabsorption - chronic pancreatitis, cystic fibrosis, coeliac disease, Crohns disease, gastric bypass surgery, small bowel resection, abnormal thyroid function 3. Bleeding disorders, currently taking anticoagulants or has received anticoagulants within 28 days of Day 1 of the trial, with the exception of low dose aspirin up to 150 mg daily* 4. Any medical procedures deemed by the principal investigator to affect study outcomes

	
 5. Known food allergies, hypersensitivity, dietary avoidance or intolerance to the study foods 6. Taking medications/supplements known to influence lipid metabolism and gastric emptying 7. On any weight-loss program 8. History of smoking during the 6 months prior to the study 9. Persons considered by the investigator to be unwilling, unlikely or unable to comprehend or comply with the study protocol. 10. Self-reported history of drug abuse or alcoholism 11. Participation in another research study within 30 days preceding the start of this study
Treatment:	
Standardised breakfast plus:
 
Test food 1: Semi-solid food – Soup (commercially available packet-soup) containing cauliflower encapsulated HiDHA® algal oil providing 400 mg DHA
 
Test food 2: Solid food – Extruded snack (savory snack) containing cauliflower encapsulated HiDHA® algal oil providing 400 mg DHA
 
Control: 2x Algal oil gel capsules containing HiDHA® algal oil providing 400 mg DHA

Study Duration:	~1 month (3 test products at least 1-week apart)
Study Population:	Healthy men
Primary Outcome:	Plasma DHA and total omega-3 LCPUFA iAUC _{0-24h}

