***Self-reported, no clinical testing will be performed.**

4. Study Design and procedures

A multi-centre, randomised, controlled, acute, 3-way cross-over single-blind study design will be used. The trial will be performed at CSIRO's Nutrition and Health Research Clinic, Adelaide (n=12) and A*STAR's Clinical Nutrition Research Centre in Singapore (n=12).

Participants will attend a screening visit to confirm their eligibility for inclusion into the trial (Figure 1). If eligible, participants will remain at the clinic where they will be enrolled into the study and participate in the first intervention on that day (Screening will be conducted at V1). After enrolment participants will attend the research clinic for test procedures on 3 occasions at least 1-week apart during which they will consume one of three test products at each occasion in random order. Participants will attend the clinic on 6 occasions in total (to include returning for 24hr blood sample) – visits 2, 4 and 6 (Figure 1). A 1-week washout period is sufficient for plasma sample to return to baseline (19). Participants will be randomly assigned by computer sequence generation (<http://www.randomisation.com>) to one of three treatment orders (Figure 1). The random allocation sequence will be generated by a staff member not involved with entering participants into the trial to ensure allocation concealment.

[figure not shown]

Figure 1. Study design

Participants will visit the research clinic on six occasions (Figure 1).

- Occasion 1: Screening + 1st intervention (randomised) involving in-clinic assessments (~9 hours).
- Occasion 2: Participants will return to the clinic for a short visit (30 minutes) where a 24-hour blood sample will be collected (Figure 2).
- Occasion 3: (1 week following Occasion 1) 2nd intervention (randomised) involving in-clinic assessments (~8.5 hours).
- Occasion 4: Participants return to the clinic for a short visit (30 minutes) where a 24-hour blood sample will be collected.
- Occasion 5: (1 week following Occasion 3) 3rd intervention (randomised) involving in-clinic assessments (~8.5 hours).
- Occasion 6: Participants return to the clinic for a short visit (30 minutes) where a 24-hour blood sample will be collected.

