Screening occasion: Participants will be pre-screened using a screening questionnaire and those determined to be potentially eligible will be invited to attend an in-clinic screening visit. After they have given signed informed consent (see details below) their eligibility will be confirmed by reviewing their medical history, demographic information and fatty fish intake obtained from the screening questionnaire, measuring height and weight and calculating BMI, and measuring vital signs (blood pressure and temperature). Eligible participants will be enrolled into the study and remain at the clinic for further 8.5 hours and complete their first intervention

Intervention occasions (Figure 2): Participants will arrive at the research clinic after an overnight fast (>10h)). Weight, percentage body fat mass and vital signs (blood pressure and temperature) will be measured, an intravenous cannula will be inserted into the participants arm for a duration of 8 hours during which the participant will remain at the research clinic.

A fasting blood sample (4 mL) will be collected after which participants will consume a standardised breakfast with their test product (see section 5 for more detail) within 15 minutes. Subsequent blood samples will be collected after 2, 4, 6 and 8 hours. The cannula will be removed, and participants will leave the research clinic. Participants will return to the research clinic the next morning after an overnight fast for collection of the 24-hour sample. The period of 24 hours was chosen as it represents an intake interval of daily intake of omega-3 supplements (19). Throughout the 9-hour day at the clinic participants will have access to low-fat snacks and a lunch meal devoid of omega-3 LCPUFA that they can consume *ad libitum* (see section 5 for more detail). Participants will leave the clinic with a take-home low-fat dinner meal.

Apart from the study specific test products, participants will be requested to maintain their habitual lifestyle patterns throughout the duration of the study and to avoid fatty fish and omega-3 LCPUFA containing supplements. Participants will be provided with a checklist to record any non-compliance or accidental consumption of these foods and return the checklist at their subsequent visit.

Staff responsible for sample and statistical analysis will be blinded to which treatment was consumed when, but participants and staff administering treatments will not be blinded.

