The Principal investigator or designee may withdraw a participant from the study at any time. In this event, the clinic will ensure the reasons have been clearly explained to the individual. Adverse event and concomitant medications will be reviewed at the time of withdrawal. A two-week follow-up will be performed for any unresolved AE at the time of withdrawal.

5. Test meals

Test meals:

1. Semi-solid food – 200 g serve Soup (commercially available packet-soup) containing cauliflower encapsulated HiDHA[®] algal oil providing 400 mg DHA + standardised breakfast
2. Solid food – 50 g serve extruded snack (savory snack) containing cauliflower encapsulated HiDHA[®] algal oil providing 400 mg DHA + standardised breakfast
3. Control: 2 x algal oil gel capsule containing HiDHA[®] algal oil providing 400 mg DHA + standardised breakfast

HiDHA[®] algal oil will be supplied by NuMega Ingredients Pty Ltd.

The standardised breakfast will consist of a small carton of Milo (Nestle: 200 ml), an apple (200 g), one muesli bar (Uncle Toby's: 24 g) (total energy = ~1600 kJ) and the test products/control.

Throughout the 8-hour day at the clinic participants will have access to low-fat snacks and a lunch meal devoid of omega-3 LCPUFA that they can consume *ad libitum*. Low-fat is defined as ≤ 3 g fat/100 g solid food or ≤ 1.5 g fat/100 ml for liquid food (20, 21). Snacks may include rice crackers, fruit, low-fat dairy products (yoghurt, chocolate milk), fruit juice, water, etc. Lunch and dinner meals will be low-fat frozen meals selected from the Lean Cuisine Steam range available in both Australia and Singapore (<https://www.vescofoods.com.au/brands/lean-cuisine>). Breakfast (selection of cereal) will be provided to participants after collection of the 24-hour sample.

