heating at 90 °C; addition of 2 mL methanol; acidification with 200 µL of acetyl chloride and heating at 90°C for 1 hr while vortexing approximately every 10min after which the samples will be returned to room temperature. Methyl esters will be extracted into 1.5 mL hexane and 1.0 µl aliquot injected onto a gas chromatographic column (DB – FastFAME, 20m x 0.18 mm from Agilent Technologies), using a PerkinElmer Clarus 690 gas chromatograph / Clarus SQ 8 T Mass Spectrometer with a split 50:1 injector. Fatty acids will be identified by comparison with authentic Sepelco 37 component FAME mix (Sigma-Aldrich, Australia) and verified using the NIST MS search database software. Peaks will be measured using TurboMass software and fatty acids will be calculated against the internal standard.

8. Statistical analysis

A sample size of n=10 per site provides >80% power to detect a difference of 10% in AUC (22). N=12 per site will be recruited to account for a 20% attrition rate.

A statistical analysis plan will be developed before statistical analysis commences. In brief, data will be presented as means and SD/SEM. Plasma DHA and total omega-3 LCPUFA concentrations will be plotted into graphs. $iAUC_{0-24h}$ (primary outcome), will be calculated using the trapezoidal rule and corrected to baseline levels. Time to maximal value (Tmax) and the maximal value (Cmax) will be determined. Primary analysis will be pairwise comparisons between test foods vs. control using linear mixed models with fixed effects for treatment, time, ethnicity and assessing the interaction of treatment*time and treatment*time*ethnicity. Participant identifier will be fitted as a random effect, i.e. one intercept per participant. Potential covariates will be identified *a priori* and included in the model (e.g. BMI). Intention-to-treat analysis will be performed primarily and per protocol analysis as secondary analysis.

Statistical analysis will be performed using appropriate statistical packages e.g. SPSS software (IBM Corporation, New York, USA). Statistical significance will be determined at a *P*-value of <0.05. Statistical analysis will be performed blinded and treatments revealed after completion of the statistical analysis.

9. Assessment of Adverse Events

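### Only three of the six possible product orders are used, so the preceding product cannot be balanced; all six orders would fit the same 24 men at no loss of precision

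*Combined protocol and SAP*

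**What the plan says.** Section 4 (Study Design and procedures) sets out the design: "A multi-centre, randomised, controlled, acute, 3-way cross-over single-blind study design will be used". At each of three intervention visits participants "consume one of three test products at each occasion in random order", but the allocation is limited: they are randomised "to one of three treatment orders (Figure 1"). The orders are in Figure 1, which is not shown in the text available for review. The text mentions neither blocking nor stratification by site.

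On carry-over, Section 4 relies on one statement: "A 1-week washout period is sufficient for plasma sample to return to baseline (19"). The reference list shows that the cited study concerned an omega-3 ethyl ester concentrate.

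Three other provisions bear on the point:

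- A pre-dose sample precedes every product (Section 4): "A fasting blood sample (4 mL) will be collected after which participants will consume a standardised breakfast".
- The primary iAUC "will be calculated using the trapezoidal rule and corrected to baseline levels" (Section 8).
- Each product is described as "algal oil providing 400 mg DHA + standardised breakfast" (Section 5).

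The Study Synopsis gives the size as "N=24 (n=12 in Australia and n=12 in Singapore"). Section 8 compares each test food with control in a mixed model with treatment, time and ethnicity terms and a participant intercept. It names no period, sequence or carry-over term and no check of pre-dose levels, and it leaves detail to a later analysis plan.

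**The concern.** In a three-period cross-over, a product given in period 2 or 3 may be measured on top of what the previous product left behind. If every product follows every other equally often, such residues are spread evenly over the comparisons. If each product always follows the same other product, they are not. A comparison of soup with capsules can then pick up a residue of the snack, which is not part of that comparison.

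The trial exists to learn whether the products differ in bioavailability. It is therefore not safe to assume in advance that their residues are equal. At stake are the two primary food-versus-control contrasts, and the ability to adjust them if a reader questions the washout.

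**Working it through.** **Inputs from the documents.** Three products, three periods and three orders (Section 4); 12 participants per site, 24 in all (Synopsis); contrasts of each food with control (Section 8). The plan gives no carry-over figure to reproduce.

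**Assumptions.** The three orders form a Latin square; all 24 complete, equally divided between orders (8 per order with three, 4 per order with six); participant and period effects are fitted; carry-over lasts one period. σ is the within-participant SD of the iAUC. S, N and C are soup, snack and control, and lS, lN and lC are what each adds to the next period's iAUC.

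**Step 1: can three orders balance the preceding product?** The six ordered pairs fall into two cycles: SN, NC, CS and SC, CN, NS. Every order supplies two pairs from the same cycle (S-N-C gives SN and NC). Three orders supply six pairs, so balance would need each pair exactly once. Each cycle has three pairs, and three cannot be made up of twos. Enumeration agrees: of the 20 sets of three orders, 2 balance period (the two Latin squares) and none balances the preceding product.

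**Step 2: bias if carry-over is ignored.** With complete, period-balanced data, each contrast is a difference of product means. Each product has a predecessor in two of its three positions.

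- Square 1 (S-N-C, N-C-S, C-S-N): soup always follows control, snack follows soup, control follows snack. The means gain 2/3 lC, 2/3 lS and 2/3 lN.
- Square 2 (S-C-N, C-N-S, N-S-C): soup follows snack, snack follows control, control follows soup.
- Six orders: each product follows each of the other two equally often, so the soup mean gains 1/3(lN + lC) and the control mean 1/3(lS + lN).

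| Design | Bias, soup − control | Bias, snack − control |
|---|---|---|
| Square 1 | 2/3(lC − lN) | 2/3(lS − lN) |
| Square 2 | 2/3(lN − lS) | 2/3(lC − lS) |
| Six orders | 1/3(lC − lS) | 1/3(lC − lN) |

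If lS = lN = lC, every entry is zero. In each square both contrasts involve the other food's carry-over.

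**Step 3: variance.** Without carry-over terms, both designs give 2σ²/24 = 0.0833 σ². With carry-over terms, least squares has 72 observations and 30 parameters (42 residual df). The variance of a carry-over contrast is 0.75 σ² with three orders and 0.1875 σ² with six. The adjusted treatment contrast subtracts the bias coefficient times the estimated carry-over difference, so:

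- three orders: 0.0833 + (2/3)² × 0.75 = 0.0833 + 0.3333 = 0.417 σ², and 0.417/0.0833 = 5.0;
- six orders: 0.0833 + (1/3)² × 0.1875 = 0.0833 + 0.0208 = 0.104 σ², and 0.104/0.0833 = 1.25.

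The standard error of a carry-over contrast is √0.75 = 0.87σ against √0.1875 = 0.43σ. A model-based test would therefore need a carry-over difference of about 2.4σ (three orders) or 1.2σ (six) for 80% power.

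**Step 4: scale.** Section 8 targets a 10% difference in AUC but gives no SD, so σ cannot be put in percentage terms. For bias alone to reach 10%, the relevant carry-over difference would have to be 10/(2/3) = 15% of AUC with three orders, or 10/(1/3) = 30% with six. For a bias of 1%, the figures are 1.5% and 3%.

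**The case against.** The strongest reply is that the risk may be negligible and the plan already contains safeguards. Much of this stands, and it rules out several stronger readings.

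- **That any carry-over biases the contrasts.** It does not. Equal carry-over cancels, all three products deliver the same oil and the same 400 mg DHA, and doses are at least a week apart.
- **That the washout is the only protection, or that carry-over cannot be checked.** The fasting samples before periods 2 and 3 show residual DHA directly, and baseline correction removes a constant residue. What is missing is a pre-specified use of those samples. Baseline correction also has limits: it does not remove a residue that is still falling, none is stated for Cmax, and the time terms in Section 8 leave open whether the primary model is fitted to corrected iAUC or to concentrations.
- **That a drifting baseline is confounded with treatment.** A drift common to all participants is balanced in a Latin square with period fitted.
- **That six orders cure the problem.** They do not. If both foods leave the same residue lF, square 1 gives a bias of 2/3(lC − lF) for soup and 0 for snack, whereas six orders give 1/3(lC − lF) for each. The total is the same and only its distribution changes.

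It is also fair to say that the 5-fold variance belongs to an analysis that Section 8 does not plan, and that Figure 1 is not available to confirm a Latin square. If its orders are not a Latin square, period balance fails as well, and Section 8 names no period term.

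None of this supplies a reason to prefer three orders. They have no precision advantage, and the text gives no justification for them.

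**Conclusion.** The point holds as a free improvement, not as a demonstrated bias. That three orders cannot balance the preceding product is certain and does not depend on Figure 1.

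The 2/3 against 1/3 coefficients, and the 5-fold against 1.25-fold variance, rest on a Latin square, 24 completers equally divided between orders, period fitted and one-period carry-over. Dropout, which the plan allows at 20%, would shift them.

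The actual bias cannot be sized from the documents and may be small. What six orders offer is a smaller coefficient, a bias confined to the two products compared, and a carry-over adjustment that remains affordable if it is ever needed.

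**What to change.** 1. In Section 4 and Figure 1, replace the three-order allocation with all six orders, in blocks of six generated separately for each site. Twelve per site divided by six gives two participants per order per site and four per order overall. The staff member not involved in enrolment can still generate the list.
2. In Section 8, add period as a fixed effect in the mixed model, distinct from sampling time.
3. In Section 8 or the later analysis plan, pre-specify a comparison of fasting pre-dose DHA across periods and by preceding product, using samples already planned.

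The cost is a new randomisation list, a revised Figure 1, a few sentences of analysis text, and an amendment approved by the ethics committee. There are no extra participants, visits or samples, and no loss of precision if carry-over is not modelled.

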Appendix

Categories of fish according to fat content

Fatty fish sources (~>500 mg LCPUFA/serve) (serve = 150 g fish / 100g canned fish)
	
 • Salmon (fresh or canned) • Mackerel • Sardines (fresh or canned) • Anchovies • Trout • Tuna (fresh or canned) • Mullet • Silver perch • Morwong • Bream • Herring • Smoked/green/blue mussels (canned) • Smoked oysters (canned)

Medium- to low-fat fish sources (<500 mg LCPUFA/serve) (serve = 150 g fish / 100g canned fish)
	
 • Yellowtail kingfish • Trevally • Snapper • Flounder • Mirror dory • Jack mackerel • Blue-spotted goatfish • Small-spotted herring • Blue-eye trevalla • Australian bass • King Dory • Wrasse • John Dory • Blue morwong • Coral trout • Blue grenadier (Hoki) • Golden perch • Ocean jacket • Leather jacket • Murray cod • Hussar • Garfish • Barramundi • Dhufish • Mangrove Jack • King George whiting • Smoked cod • Flathead • Shark (Flake) • Jackass morwong • Squid/calamari (100g) • Oysters, raw (100g) • Scallops (100g) • Prawn (100g) • Octopus (10) • Crab (100g) • Lobster/crayfish (100g) • Moreton bay bug (100g) • Whiting

Source: Australian Heart Foundation

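### The LCPUFA-free condition on clinic food is not extended to the take-home dinner, and non-fatty fish and seafood are not excluded around the test days

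*Combined protocol and SAP*

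**What the plan says.** All references are to the combined protocol and SAP.

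- **Clinic food.** Section 4 (Intervention occasions) states that "participants will have access to low-fat snacks and a lunch meal devoid of omega-3 LCPUFA". Section 5 (Test meals) repeats the condition for the clinic day.
- **Dinner.** Section 4: "Participants will leave the clinic with a take-home low-fat dinner meal". Section 5 adds: "Lunch and dinner meals will be low-fat frozen meals selected from the Lean Cuisine Steam range available in both Australia and Singapore". Neither section attaches the LCPUFA-free condition to dinner.
- **Meaning of low-fat.** Section 5: "Low-fat is defined as ≤ 3 g fat/100 g solid food". This limits total fat, not LCPUFA.
- **Other food.** Under section 4, participants keep to their usual habits except that they are asked "to avoid fatty fish and omega-3 LCPUFA containing supplements". A checklist records lapses concerning those foods.
- **Fish categories.** The Appendix defines fatty fish as roughly above 500 mg LCPUFA per serve. About 40 further fish and seafood items fall under "Medium- to low-fat fish sources (<500 mg LCPUFA/serve". No section restricts these during the study.
- **Sampling and outcome.** Blood is taken at 0, 2, 4, 6, 8 and 24 h, the last after an overnight fast (section 4). The primary outcome is plasma DHA and total omega-3 LCPUFA iAUC over 0–24 h (section 2), by the trapezoidal rule with baseline correction (section 8).

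**The concern.** By making the lunch LCPUFA-free, the plan treats background LCPUFA as something that can distort the outcome. The same control is not written for the rest of the 24 h window. A participant who follows the stated avoidance rule exactly could eat a serve of white fish or prawns that evening, or the evening before, and apparently have nothing to enter on the checklist.

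The two evenings act in opposite directions. LCPUFA eaten after the 8 h sample can raise the 24 h value, and with it iAUC. LCPUFA eaten the evening before can raise the fasting value, which is subtracted, and so lower iAUC. Neither effect has anything to do with the test product. If the intake is not recorded, it cannot be identified or allowed for afterwards. The trial plans on 10 evaluable participants per site and a 10% difference in AUC (section 8), so avoidable noise matters.

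**Working it through.** The plan gives no figure to reproduce here. The check sets the food rules against each other and then works out which samples are exposed.

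**1. Does the low-fat rule keep LCPUFA out?** Inputs: 3 g fat per 100 g (section 5); a serve of 150 g fish or 100 g canned fish, and the 500 mg cut-off (Appendix).
- 150 g serve: 150 × 3/100 = 4.5 g fat allowed; 0.5/4.5 = 11%.
- 100 g serve: 100 × 3/100 = 3.0 g fat allowed; 0.5/3.0 = 17%.

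An amount of LCPUFA at the category ceiling fits within the fat limit, so the low-fat rule does not exclude it.

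**2. Size relative to the dose.** 500/400 = 1.25. This is an upper bound: it takes the ceiling of the whole category, and it sets total LCPUFA against a dose stated as DHA. It is a ratio of amounts eaten and does not convert into a percentage of iAUC.

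**3. Which samples are exposed?** Each trapezoid weight is half the width of the adjoining intervals.

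| Time (h) | 0 | 2 | 4 | 6 | 8 | 24 |
|---|---|---|---|---|---|---|
| Weight (h) | 1 | 2 | 2 | 2 | 9 | 8 |

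The weights sum to 24.
- *Dinner on the test day.* The 8 h sample is taken before the participant leaves, so only the 24 h sample can be affected: 8/24 = 33% of the time weight. Each extra 1 µg/mL at 24 h adds 8 µg·h/mL to iAUC.
- *Evening before.* If the baseline is subtracted over the whole 24 h with negative increments kept (an assumption; section 8 does not give the detail), the net weight of the fasting sample is 1 − 24 = −23 h. A 1 µg/mL rise in the fasting value that has gone by 2 h lowers iAUC by 23 µg·h/mL. A rise that persists all day cancels and has no effect. The range is 0 to 23.

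**4. Illustration only.** The documents give no plasma profile and no figure for the rise that a serve of fish would cause at 24 h. Two assumed profiles of increments (µg/mL at 0, 2, 4, 6, 8, 24 h) are used:
- A: 0, 5, 15, 20, 15, 5 gives 10 + 30 + 40 + 135 + 40 = 255 µg·h/mL.
- B: 0, 3, 10, 12, 10, 6 gives 6 + 20 + 24 + 90 + 48 = 188 µg·h/mL.

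| Assumed rise at 24 h (µg/mL) | Added iAUC (µg·h/mL) | % of A | % of B |
|---|---|---|---|
| 1 | 8 | 3.1 | 4.3 |
| 2 | 16 | 6.3 | 8.5 |
| 5 | 40 | 15.7 | 21.3 |

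These are shifts in one participant's iAUC on one occasion. If one of 10 participants at a site were affected for one product, that product's mean at the site would move by a tenth of this, about 0.3% to 2.1%.

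**The case against.** The strongest reply is that dinner is not left to the participant. Section 5 makes it a study-supplied frozen meal from the same range as the LCPUFA-free lunch, and the documents do not say whether that range contains any fish or seafood. This stands. A reader might infer that any low-fat dinner will do, or that the supplied dinner contains LCPUFA; the text supports neither. What remains is that lunch carries an LCPUFA condition beyond its source and dinner does not, that no section tells participants to eat only the supplied dinner, and that no meal is supplied for the evening before.

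Secondly, not forbidding a food is not the same as endorsing it. The checklist wording on non-compliance could be read broadly, and the test-day figure, which is not shown, may carry a fuller instruction. This also stands in part: such fish is best described as not prohibited and apparently not recorded.

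Thirdly, a reader might infer that the soup or snack comparison with the capsules is biased. The documents do not support that. Treatment order is random, comparisons are within participants, and nothing suggests that evening fish intake would depend on the product consumed.

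Finally, stricter control on the evening before is a design improvement, not an inconsistency in the plan, which already asks for a fast of more than 10 h. That is fair. But the fasting sample enters every increment, and the first test day falls on the day of consent and enrolment, with no dietary instruction stated for the evening before it.

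**Conclusion.** The point holds as a gap in dietary control that is cheap to close. The LCPUFA-free condition stops when the participant leaves the clinic. Fish and seafood below 500 mg LCPUFA per serve are not excluded after the 8 h sample or on the evening before a test day.

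On the test-day evening the exposure is confined to the 24 h sample, 33% of the trapezoid time weight; on the evening before, it acts through the baseline. The effect on iAUC cannot be sized from the documents. The percentages in the illustration depend wholly on the assumed profiles and rises.

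The expected consequence is mainly extra within-participant variability, and so some loss of precision. A systematic effect is possible between sites if habitual intake of these foods differs. Each site recruits one ethnicity, so such a difference could not be separated from ethnicity. A constant shift common to all three products would drop out of the differences from control but would remain in an overall comparison of ethnicities. Whether habitual intake does differ is not stated.

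**What to change.** 1. In sections 4 and 5, state that the take-home dinner, like lunch, is free of omega-3 LCPUFA, and choose the meals within the range accordingly.
2. Ask participants to avoid fish and seafood of every Appendix category, as well as LCPUFA supplements, from the evening before each test day until the 24 h sample. Give this instruction for the first test day at the pre-screening contact, because consent and the first intervention fall on the same day.
3. Add these foods to the existing checklist, covering both evenings, so that any intake is on record.

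The cost is wording in the protocol, participant instructions and checklist. No visit, sample or assay is added. The downside is a slightly stricter diet around three test days.

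### The evening before each test day is neither standardised nor recorded, which adds avoidable within-man noise to the fasting value subtracted in the primary iAUC

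*Combined protocol and SAP*

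**What the plan says.** Section 4 (Intervention occasions) states that, the test products aside, "participants will be requested to maintain their habitual lifestyle patterns throughout the duration of the study". The same sentence then adds one dietary restriction: "and to avoid fatty fish and omega-3 LCPUFA containing supplements". Men also arrive fasted for more than 10 hours. They receive a "checklist to record any non-compliance or accidental consumption of these foods"; it covers the fish and supplement restriction and nothing else about the day before.

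Food after dosing is much more tightly controlled. Breakfast is standardised (Section 5). Lunch and snacks are supplied, low in fat and, for lunch at least, free of omega-3 LCPUFA, although eaten ad libitum. For the evening: "Participants will leave the clinic with a take-home low-fat dinner meal".

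The first test day is also the screening and consent day: eligible men "participate in the first intervention on that day (Screening will be conducted at V1". The evening before it therefore precedes enrolment.

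The Appendix keeps a class of fish outside the restriction, "Medium- to low-fat fish sources (<500 mg LCPUFA/serve", while each test product provides 400 mg DHA (Section 5).

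Section 8 computes iAUC0-24h by the trapezoidal rule, corrected to baseline, from samples at 0, 2, 4, 6, 8 and 24 hours. The model has one random intercept per participant. BMI is the only covariate named, and that as an example.

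**The concern.** The outcome is an absolute plasma concentration in µg/mL. If a man's fasting level differs between his three test days because of what he ate, drank or did the evening before, the correction carries that difference into his iAUC even when DHA absorption is identical. There is one fasting sample per test day, so nothing averages it out. The random intercept absorbs stable differences between men but not a shift specific to one visit.

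At stake is the precision of the within-man comparison between each test food and the capsules. The crossover depends on that precision, with 10 evaluable men planned per site. Extra noise would make a null result harder to interpret for the hypothesis that the vegetable carrier has no effect on bioavailability.

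**Working it through.** **1. The plan's own figure.** Section 8 gives more than 80% power with n=10 per site for a 10% difference in AUC, but no SD, so the power cannot be reproduced. Solved backwards (paired t-test, two-sided 0.05 assumed), 10 men give 80% power only if the SD of the paired differences is at most 10.0% of the mean. I take the 10% to apply to iAUC.

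**2. Weight of the fasting sample.** For samples at 0, 2, 4, 6, 8 and 24 h the trapezoid weights are 1, 2, 2, 2, 9 and 8 (sum 24). Baseline correction subtracts 24 × C(0), so the net weight of the fasting value is 1 − 24 = −23. This assumes net iAUC, with area below baseline counted as negative.

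**3. Allowing the shift to persist.** Let a 1 µg/mL fasting shift decay as d(t) = 2^(−t/h), where h is its half-life. The change in iAUC is Σ w(t)·d(t) − 24. For h = 4 h: 1 + 2(0.707) + 2(0.5) + 2(0.354) + 9(0.25) + 8(0.016) − 24 = −17.5.

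The documents give no mean iAUC. I assume an average DHA rise of 5–15 µg/mL over 24 h, that is 5 × 24 = 120 to 15 × 24 = 360 µg·h/mL.

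| Shift of 1 µg/mL | Change in iAUC (µg·h/mL) | As % of 360 | As % of 120 |
|---|---|---|---|
| gone by 2 h | −23.0 | 6.4 | 19.2 |
| half-life 4 h | −17.5 | 4.9 | 14.6 |
| half-life 12 h | −10.6 | 2.9 | 8.8 |
| half-life 24 h | −6.5 | 1.8 | 5.4 |
| lasts all day | 0 | 0 | 0 |

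**4. What noise would do to power.** Let r be the extra per-visit SD as a percentage of mean iAUC, so that SD_diff² = s0² + 2r². Start from exactly 80% power without it.

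| r | Power, n=10 (s0 = 10.04%) | n for 80% | Power, 20 pooled (s0 = 15.14%) |
|---|---|---|---|
| 2% | 77% | 11 | 79% |
| 5% | 63% | 14 | 72% |
| 10% | 37% | 26 | 53% |

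**5. Linking steps 3 and 4.** For r = 5%, the between-visit SD of the fasting shift would have to be 0.05 × 120/23 = 0.26 to 0.05 × 360/23 = 0.78 µg/mL if the shift is gone by 2 h, but 0.05 × 120/6.5 = 0.92 to 0.05 × 360/6.5 = 2.8 µg/mL at a half-life of 24 h. The documents do not show where the real value lies.

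**The case against.** Several stronger readings are tempting, and the documents do not support them.

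- **Bias between products.** Order is randomised, so day-before variation falls on the products by chance. This assumes that the three orders place each product once in each position (Figure 1 could not be seen). Chance imbalance remains possible with 10–12 men per site, but the expected effect is noise.
- **The full weight of 23 as the typical effect.** It applies only if the shift has gone by 2 h. Baseline correction removes the part that persists through the day, so it is itself partial protection. The protection is incomplete: a shift that lasts through 8 h but is absent at 24 h still leaves 16 − 24 = −8 µg·h/mL.
- **A distorted curve because 0 h follows a usual dinner and 24 h a supplied one.** The average mismatch applies to all three products and largely cancels in contrasts with control. The ethnicity objective in Section 2 is also framed relative to control. The second hypothesis is not, but the documents say nothing about how usual dinners differ between sites. Nor does Section 4 say that the take-home dinner must be eaten.
- **A wholly unrestricted evening.** The fast and the restriction on fatty fish and supplements apply, and a request to keep habitual patterns does not invite an unusual evening. The gap is the rest of the meal (including lower-fat fish), alcohol and exercise.
- **An underpowered trial.** No between-visit SD of fasting DHA is given, and the variability in the study cited for the sample size may already include this noise.

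Other features also protect precision: the standardised breakfast and the analysis of each man's samples in one run (Section 7). Figure 2 and the consent documents were not available for this check; a day-before instruction there would answer the point to that extent.

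**Conclusion.** The gap stands as a precision issue. In the readable text, nothing standardises or records the prior evening's meal (beyond fatty fish and supplements), alcohol or exercise, and the primary outcome is sensitive to one fasting sample. A 1 µg/mL fasting shift is worth 0–19% of iAUC on the assumed mean of 120–360 µg·h/mL, depending on how long it lasts, against a 10% target difference. The mechanism and the trapezoid weights follow from the plan. The mean iAUC, the size of real shifts and their persistence are assumptions, so no loss of power has been demonstrated. The change is worth making before enrolment because it is inexpensive and a fasting sample cannot be retaken once the test day has passed.

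**What to change.** Keep the habitual-lifestyle rule for other days and add a rule for test days in Section 4:

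- Each man records his evening meal before the first test day and repeats it before the second and third. The supplied low-fat frozen dinner is an alternative only if it can also be used before the first test day; otherwise the three baselines would follow unlike meals.
- He avoids alcohol and strenuous exercise from the day before each test day until the 24-hour sample.
- Evening meal, alcohol and exercise are added to the existing checklist.
- Because the first test day is the screening and consent day, the request goes out with the fasting instruction that men already need at pre-screening. Meal, alcohol and exercise for that first evening are recorded at Visit 1.

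The cost is instruction and checklist wording, slightly more participant burden, a somewhat less habitual setting, and at most three extra frozen meals per man if that option is used. Sampling times and outcomes are unchanged.
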